### Biomarker Monitoring

The following biomarkers will be evaluated: Haptoglobin (Hp), Ferritin and bilirubin, Hemopexin, IL-10, Heme Oxygenase 1 (HO-1) and P21, as well as urine biomarker response to SnPP. Biomarkers will be measured at baseline and 2, 4, 8, 12, 18, 24, 48, 72, 96 and 168 hours after administration of SnPP. All biomarkers will be measured at the same time points.

Protocol Number: REN-003 (Original)

Date: 25 March 2019

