#### **Statistical Considerations**

**Sample Size**: No formal sample size calculation has been performed for this phase 1b study. However, it is believed that six subjects per dose group in the healthy volunteer cohorts (3) and the CKD stages 3 & 4 cohorts (2 each) will be adequate to establish POC based on biomarker response and identify an optimal dose for further testing, recognizing that a battery of different surrogate biomarkers will be evaluated

**Analysis Populations and General Methodology:** All subjects who receive study medication will be included in the Safety population for safety analysis. Subjects who receive study medication and have a post-baseline efficacy assessment will be included in the Modified Intent-

CONFIDENTIAL Page 12 of 38

Protocol Number: REN-003 (Original)

Date: 25 March 2019

to-Treat (MITT) population for efficacy analysis. All subject data will be listed. When appropriate, summary statistics will be provided (number of non-missing values, mean, median, standard deviation, minimum, and maximum for continuous variables and number and percentage of subjects for categorical variables) by treatment group for all measures, including demographic and baseline assessments, safety, and efficacy endpoints. Baseline for all safety and efficacy endpoints is defined as the last observations before administration of the first IV infusion of study drug. No imputation will be used for missing data.

**Safety Analysis:** Safety measures including AEs, infusion-related reactions, clinical laboratory tests, vital signs, physical exams, and concomitant medication usage will be summarized descriptively by treatment group and study visit, where appropriate.

**Biomarker Analysis:** Biomarker response will be summarized by treatment group and study visit, comparing change from baseline at 2, 4, 8, 12, 18, 24, 48, 72, 96 and 168 hours after start of infusion.

Percent change from baseline will be analyzed using the mixed model for repeated measures (MMRM). The between-group comparison will be performed using the simple contrast at 2, 4, 8, 12, 18, 24, 48, 72, 96 and 168 hours post-dosing

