4 EFFICACY, PHARMOCOKINETIC, AND SAFETY VARIABLES

Efficacy Variables

- Percent change from baseline in biomarkers at each postbaseline time point
- Change from baseline in biomarkers at each postbaseline time point

The biomarkers include the following pharmacodynamic variables

- Haptoglobin (Hp)
- Ferritin
- Bilirubin
- Hemopexin
- IL-10
- Heme Oxygenase 1 (HO-1)
- P21

The urine biomarkers include the following pharmacodynamic variables

- Hemopexin
- Ferritin
- P21
- Heme-Oxygenase 1 (HO-1)

Pharmacokinetic (PK) Variables

- Maximum serum concentration (C_{max})
- Time to maximum serum concentration (T_{max})
- Area under the concentration-time curve from 0 to last time point (AUC_{0-t})
- Area under the concentration-time curve from 0 to infinity (AUC_{0-inf})
- Terminal elimination rate constant (λ_z)
- Terminal elimination half life (T_{1/2})
- Clearance (CL)
- Volume of distribution (V_z)

- Renal excretion and renal clearance (CL) of tin

Safety Variables

- Treatment-emergent adverse events
- Infusion-related reactions
- Clinical laboratory tests
- ECG
- Vital signs
- Physical exams
- Concomitant medications

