7.1.1.3 Adverse Event Severity or Relationship to Study Drug

If severity of an AE is not reported, then for tables of AEs by severity, the event will be classified as 'Severe' and clearly footnoted. If relationship to study drug is not reported for an AE, then for tables of study-drug related AEs, the event will be assigned the relationship of 'definite'. Tables presenting related AEs will include all AEs with relationships of 'possible', 'probable' or 'definite' as assessed by the investigator or defined as 'definite' when no investigator assessment is made.

7.1.2 *Multiplicity Adjustments*

Not applicable.

7.1.3 *By-Center Analyses*

This is a single-center study.

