7.6 Efficacy Analysis

7.6.1 *Percent Change in Response Biomarkers*

The efficacy endpoint is the percent change (PCH_T) in each response biomarker relative to the Baseline period.

PCH_T will be calculated as $100 \times (T - B)/B$, where T and B are Response biomarker at 2, 4, 8, 12, 18, 24, 48, 72, 96 and 168 hours post dose (T) and baseline period (B).

PCH_T will be analyzed using a Mixed-Effect Model for Repeated Measure (MMRM) as follows:

- A 2-way MMRM pooling stage 3 and stage 4 CKD patients and healthy subjects together
- A 2-way MMRM pooling stage 3 and stage 4 CKD patients together
- A 2-way MMRM for Healthy subjects

The model will include dose level, visit (2, 4, 8, 12, 18, 24, 48, 72, 96 and 168 hours), and dose-by-visit interaction as factors and baseline response biomarker as covariate. The model parameters will be estimated using the restricted maximum likelihood method with the toeplitz variance-covariance matrix and Kenward-Roger estimate for the denominator degrees of freedom. The between dose comparison will be performed using contrast in the main effect and the simple contrast at each time point. Least squares mean (LSM) and the associated 95% confidence interval (CI) for each dose level will be presented. The difference in LSM between doses and the 95% CI for the difference will also be presented. Results will be presented for the pooled population, as well as for the CKD and healthy populations separately.

Additionally, LSM for each dose group will be plotted over time for the CKD patients and healthy volunteers pooled population as well as for each population separately. Dose response relationship will be examined graphically and may be analyzed where appropriate.

A sample SAS code is provided as follows. The code assumes that “visit” has 10 values (2, 4, 8, 12, 18, 24, 48, 72, 96 and 168 hours), “dose” is coded as 1 = 9 mg SnPP, 2 = 27 mg SnPP, and 3 = 90 mg SnPP, “ckd” is coded as 2= CKD patients and healthy volunteers pooled, 1 = patients with CKD, 0 = healthy volunteers, and “resp” = PCH_T, the % change from baseline being analyzed.

```
ODS OUTPUT LSMEANS=lsm DIFFS=diff ESTIMATE=estm;
PROC MIXED DATA=XXXX;
BY ckd;
CLASS dose usubjid visit;
MODEL resp = base visit dose dose*visit / DDF=KR;
REPEATED visit / SUBJECT=usubjid(dose) TYPE=UN;
ESTIMATE "90 mg v 27 mg overall" dose 1 0 -1;
LSMEANS dose / DIFF CL;
ESTIMATE "90 mg v 27 mg @ 168 hours " dose 0 -1 1
dose*visit 0 0 0 0 0 0 0 0 0 0
0 0 0 0 0 0 0 0 0 -1

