8 SAMPLE SIZE CALCULATIONS

No formal sample size calculation has been performed for the study. However, it is believed that 6 subjects per dose group will be adequate to establish differences in biomarker response between groups.

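### SAP 7.1.2 calls multiplicity not applicable, although SAP 7.6 plans roughly 1,100 to 3,100 between-dose biomarker comparisons, names none as key and labels only the CMH tests exploratory

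*SAP*

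**What the plan says.** SAP 7.1.2 (Multiplicity Adjustments) reads, in full, "Not applicable". No reason is given.

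SAP 4 lists the response markers under Efficacy Variables. There are seven in blood ("The biomarkers include the following pharmacodynamic variables") and four in urine ("The urine biomarkers include the following pharmacodynamic variables").

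SAP 7.6.1 fits an MMRM to percent change, with "visit (2, 4, 8, 12, 18, 24, 48, 72, 96 and 168 hours" as the visits. Doses are compared on the main effect and at each time point, for the pooled, CKD and healthy populations, and "The difference in LSM between doses and the 95% CI for the difference will also be presented". SAP 7.6.2 repeats this on absolute change. SAP 7.6.3 adds responder odds ratios between doses at each time point. SAP 7.6.4, the only part headed exploratory, adds CMH tests of 90 v 27 mg at each time point.

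The biomarker effect and the optimal dose are two of the four primary objectives (SAP 2). SAP 8 states that "it is believed that 6 subjects per dose group will be adequate to establish differences in biomarker response between groups". The protocol (synopsis, Sample Size; section 11.6) believes the group size adequate to establish proof of concept from biomarker response and to identify an optimal dose, "recognizing that a battery of different surrogate biomarkers will be evaluated".

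**The concern.** Multiplicity plainly arises here, so dismissing it without explanation leaves the reader with no rule for interpreting the output. An exploratory trial need not adjust, but the plan should then say that it is exploratory. SAP 7.7 does this for safety by declaring that no inferential statistics are planned. SAP 7.6 has no such statement for the MMRM or responder results.

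At stake is what may be concluded. The plan names no key comparison and gives no rule for reading many markers together. Nothing in it therefore prevents a few nominally significant dose contrasts from being reported as proof of concept, or used to choose a dose for later testing, even if the doses do not differ.

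**Working it through.** The documents give no alpha, power or calculated sample size, so there is no figure of theirs to reproduce.

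**Inputs**
- Markers: 7 blood + 4 urine = 11 (SAP 4).
- Time points: 10 (SAP 7.6.1). The protocol synopsis says "All biomarkers will be measured at the same time points", but protocol 9.6.3 to 9.6.5 schedule urine response samples only at baseline and then on Days 2, 3, 4, 5 and 8. That gives 5 post-dose urine time points.
- Dose pairs: pooled 3 + CKD 1 (27 and 90 mg only) + healthy 3 = 7. In the SAP 7.6.1 sample code, the only per-visit estimate is 90 v 27 mg, which suggests a narrower reading of one pair in each of 3 populations.
- Assumption: 5% two-sided per comparison, taken from the 95% intervals.

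**Count per marker, all pairs, 10 time points**
- MMRM: 7 pairs x (10 + 1) contrasts x 2 scales = 154
- Responder: 7 x 10 = 70
- CMH: 3 populations x 10 x 2 scales = 60
- Total: 284

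| Reading | Comparisons |
|---|---|
| 11 markers, all pairs, 10 time points | 284 x 11 = 3,124 |
| Same, urine at 5 time points | 284 x 7 + 149 x 4 = 2,584 |
| Blood markers only, all pairs | 284 x 7 = 1,988 |
| 11 markers, 90 v 27 mg only | 156 x 11 = 1,716 |
| Same, urine at 5 time points | 156 x 7 + 81 x 4 = 1,416 |
| Blood markers only, 90 v 27 mg only | 156 x 7 = 1,092 |

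With 5 time points and all pairs, the per-marker total is 84 + 35 + 30 = 149. For 90 v 27 mg only it is 66 + 30 + 60 = 156 at 10 time points and 36 + 15 + 30 = 81 at 5.

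**Chance of at least one nominal false positive when the doses do not differ**

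*Narrow case:* healthy volunteers, 6 per dose, 90 v 27 mg, 7 blood markers x 10 visits = 70 contrasts, one scale, 15 degrees of freedom.
- If all 70 were independent: 1 - 0.95^70 = 0.97. They are not, so this is too high.
- Simulated, correlation decaying over the actual sampling hours with a correlation time of 24 or 72 h, between-marker correlation 0 or 0.3: 0.81 to 0.93.
- Simulated with very slow decay (correlation time about 300 h, between-marker correlation 0 to 0.6): 0.51 to 0.66.
- The expected number is 70 x 0.05 = 3.5 under any correlation. High correlation clusters the false positives in fewer trials.

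*Wider case:* all 7 population-dose pairs, 11 contrasts each, one MMRM scale (77 per marker).
- 7 markers (539 contrasts): 0.74 to 1.00. 11 markers (847 contrasts): 0.77 to 1.00.
- The chance is at least 0.92 wherever between-marker correlation is 0.6 or less. It falls below 0.80 only when both time correlation (0.9 or more) and marker correlation (0.9) are extreme.

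**Price of formal control over the 7 blood markers** (6 v 6, 15 degrees of freedom, one contrast per marker)
- Unadjusted and independent: 1 - 0.95^7 = 0.30.
- At Holm's first step, 0.05/7 = 0.0071, the difference detectable with 80% power rises from 1.73 to 2.32 SD. Power at 1.73 SD falls from 80% to about 48%.

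**The case against.** The strongest defence is the setting. This is an open-label Phase 1b dose escalation with six subjects per group, no formal sample size and markers described as potential surrogates. Leaving such comparisons unadjusted is ordinary practice, and MMRM and responder results shown as estimates with intervals are not a testing scheme. This stands, and it is why the remedy is a statement of status rather than a compulsory adjustment. It does not rescue the two-word entry, because the SAP never says the MMRM and responder analyses are exploratory and SAP 8 says the opposite.

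A reader might infer that the plan runs some 3,100 tests at 5%, with 0.05 x 3,124 = 156 false positives expected and one all but certain. The documents do not support that. They state no alpha. The figure 3,124 is near the top of the range, and 660 of those comparisons are CMH tests already headed exploratory. Exact 5% size cannot be assumed for responder models and quintile-stratified CMH tests with six per dose. Strong correlation also lowers the chance of any false positive.

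A reader might also infer that the battery of markers is there to buy extra chances of a hit, or that a single hit would be called proof of concept. Neither is written. A battery can equally be read for agreement across related markers. The battery and proof-of-concept wording is in the protocol, and SAP 8 does not repeat it. What remains is that neither document gives a rule for reading the markers together.

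**Conclusion.** The point holds as a gap in labelling and interpretation. SAP 7.1.2 is wrong to treat multiplicity as not applicable when SAP 7.6 plans about 1,100 to 3,100 correlated between-dose comparisons with none named as key, and when the documents claim the data will establish proof of concept and differences between groups.

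At least one nominal false positive is likely: about 0.8 to 0.9 in the narrow healthy-volunteer case under moderate correlation, about 0.5 to 0.7 if values change very slowly over time, and higher for the full set. These figures assume a two-sided 5% reading of the 95% intervals and no true dose difference for any marker. That null may well be false for some markers, since the protocol describes SnPP as a heme oxygenase inhibitor and bilirubin is on the list. It is nevertheless the case a proof-of-concept claim must exclude.

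**What to change.** Replace the entry in SAP 7.1.2 with text to this effect:

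> No adjustment for multiplicity is made. All biomarker comparisons (MMRM, responder and CMH) are exploratory and are reported as estimates with nominal 95% confidence intervals. No proof-of-concept or optimal-dose claim will rest on an isolated nominally significant contrast.

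In SAP 8, change the wording about establishing differences to exploring them. Make the matching change to the proof-of-concept wording in the protocol synopsis and section 11.6. Reconcile the urine sampling times between the synopsis and sections 9.6.3 to 9.6.5.

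If the sponsor wants a confirmatory proof-of-concept claim, it should instead name a small set of key biomarker measures, each with its scale, population and time window, before the results are seen, and control error over that set. Two choices need care. The protocol ties proof of concept to biomarker response, so a between-dose contrast could miss an active drug with similar responses at 27 and 90 mg. An average over 2 to 168 hours could also dilute a short-lived response.

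The first route costs only wording, and isolated nominal positives can no longer be presented as proof of concept. The second costs power, for example from 80% to about 48% at 1.73 SD with Holm's first step over seven markers.

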7.2 Subject Disposition

Subject disposition will be tabulated by dose group and overall and will present the number and, when appropriate, percentage of subjects who were:

- Enroled
 - Not treated
 - Treated
- In the safety analysis set
- In the PK analysis set
- In the MITT analysis set
- Completed the study as planned

- Discontinued from the study, and
- Reasons for discontinuation from the study

Percentages for all rows will use the number of subjects treated as the denominator.

The reasons for exclusion of subjects from the MITT and PK analysis set will be included in the data listing.

Data will be summarized for each dose group and overall as well as by stratum (CKD Stage 3 patients and CKD Stage 4 patients versus healthy volunteers).

Note that the reasons for exclusion of a subject from the MITT and PK analysis set are not mutually exclusive, thus a subject may be excluded for multiple reasons.

7.3 Description of Demographics and Baseline Characteristics

7.3.1 *Demographics*

The summary of demographic data will present:

- Age (years) – descriptive statistics
- Sex – n (%)
- Ethnicity – n (%)
- Race – n (%)

Age is calculated from the date the subject signed the informed consent form (ICF) and birth. It is presented as the number of years, rounding down to the nearest integer year. For partial birthdates, impute the first of the month for missing day and January for missing month to calculate age. It is presumed that birth year is known.

The demographic summary will present the data for each dose group and overall as well as by stratum (CKD Stage 3 patients and CKD Stage 4 patients versus healthy volunteers). Summaries will be provided for all (safety, MITT and PK) analysis sets.

7.3.2 *Baseline Characteristics*

The summary of baseline characteristic data will present:

- Physical examination and weight
- Electrocardiogram

Descriptive statistics (n, mean, SD, median, minimum and maximum) will be provided by dose group for the Safety Analysis Set.

7.4 Prior and Concomitant Medications

Prior and concomitant medications will be coded using the World Health Organization Drug Dictionary (WHODD version March 2019) and will be classified according to the default anatomical therapeutic chemical (ATC) classification and preferred term.

Prior medications are defined as medications with a stop date and time prior to the start of study drug administration.

Concomitant medications are defined as medications taken after the start of study drug administration (i.e., started prior to the start of study drug administration and continued after or started after the start of study drug administration).

Prior and concomitant medications will be summarized separately using n (%) of subjects for each dose group by ATC class and preferred term for the safety analysis set.

Subjects may have more than one medication per ATC class and preferred term. At each level of subject summarization, a subject will be counted only once if one or more medications are reported by the subject at the same level.

7.5 Measurements of Treatment Compliance

Study treatment is administered by the site personnel other than the subject him/herself, therefore compliance is assured.

7.6 Efficacy Analysis

7.6.1 *Percent Change in Response Biomarkers*

The efficacy endpoint is the percent change (PCH_T) in each response biomarker relative to the Baseline period.

PCH_T will be calculated as $100 \times (T - B)/B$, where T and B are Response biomarker at 2, 4, 8, 12, 18, 24, 48, 72, 96 and 168 hours post dose (T) and baseline period (B).

PCH_T will be analyzed using a Mixed-Effect Model for Repeated Measure (MMRM) as follows:

- A 2-way MMRM pooling stage 3 and stage 4 CKD patients and healthy subjects together
- A 2-way MMRM pooling stage 3 and stage 4 CKD patients together
- A 2-way MMRM for Healthy subjects

The model will include dose level, visit (2, 4, 8, 12, 18, 24, 48, 72, 96 and 168 hours), and dose-by-visit interaction as factors and baseline response biomarker as covariate. The model parameters will be estimated using the restricted maximum likelihood method with the toeplitz variance-covariance matrix and Kenward-Roger estimate for the denominator degrees of freedom. The between dose comparison will be performed using contrast in the main effect and the simple contrast at each time point. Least squares mean (LSM) and the associated 95% confidence interval (CI) for each dose level will be presented. The difference in LSM between doses and the 95% CI for the difference will also be presented. Results will be presented for the pooled population, as well as for the CKD and healthy populations separately.

Additionally, LSM for each dose group will be plotted over time for the CKD patients and healthy volunteers pooled population as well as for each population separately. Dose response relationship will be examined graphically and may be analyzed where appropriate.

A sample SAS code is provided as follows. The code assumes that “visit” has 10 values (2, 4, 8, 12, 18, 24, 48, 72, 96 and 168 hours), “dose” is coded as 1 = 9 mg SnPP, 2 = 27 mg SnPP, and 3 = 90 mg SnPP, “ckd” is coded as 2= CKD patients and healthy volunteers pooled, 1 = patients with CKD, 0 = healthy volunteers, and “resp” = PCH_T, the % change from baseline being analyzed.

```
ODS OUTPUT LSMEANS=lsm DIFFS=diff ESTIMATE=estm;
PROC MIXED DATA=XXXX;
BY ckd;
CLASS dose usubjid visit;
MODEL resp = base visit dose dose*visit / DDF=KR;
REPEATED visit / SUBJECT=usubjid(dose) TYPE=UN;
ESTIMATE "90 mg v 27 mg overall" dose 1 0 -1;
LSMEANS dose / DIFF CL;
ESTIMATE "90 mg v 27 mg @ 168 hours " dose 0 -1 1
dose*visit 0 0 0 0 0 0 0 0 0 0
0 0 0 0 0 0 0 0 0 -1
0 0 0 0 0 0 0 0 0 1 / CL;
RUN;
ODS OUTPUT CLOSE;
```

Note: Depending on the convergence status in the computation, Toeplitz (toep), 1st order autoregressive AR(1), and compound symmetry (CV) variance-covariance matrix will be applied sequentially. The final analysis will be based on the first matrix leading to the convergence in the computation.

7.6.2 *Absolute Change*

In addition to the percent changes from baseline, absolute change from baseline will also be analyzed using MMRM. The method of analysis will be identical after replacing variable “resp” with “T-B” in [Section 7.6.1](#).

7.6.3 *Responder Analysis*

Repeated measures responder analyses will be fitted using the generalized estimating equations (GEE) with PROC GENMOD in SAS for the proportion of patients reporting a response (defined as a 50% or greater reduction in each response biomarker from baseline) at each Visit.

The model set up is similar to MMRM ([Section 7.6.1](#)). A logit link function will be used for this binary response variable. The unstructured within-subject variance-covariance matrix will be assumed. If computational convergence is an issue, other types of variance-covariance matrices will be explored. Odds ratios and 95% confidence intervals will be presented comparing proportion of responders between dose levels at each assessment timepoint. Results will be presented for the pooled population, as well as for the CKD and healthy populations separately.

Sample SAS code is given below. Variable “resp” is coded as 1 = Responder and 0 = Non-Responder.

```
ODS OUTPUT LSMEANS=lsm DIFFS=diff ESTIMATE=estm;
PROC GENMOD DATA=dataset;
  BY ckd;
  CLASS visit dose usubjid;
  MODEL resp(EVENT='1') = base visit dose dose*visit / LINK=LOGIT DIST=BIN;
  REPEATED SUBJECT = usubjid /TYPE=UN;
  LSMEANS dose / DIFF CL;
RUN;
ODS OUTPUT CLOSE;
```

7.6.4 *Exploratory analysis*

Percent change and change in each response biomarker will be analyzed using the Cochran-Mantel-Haensel (CMH) test stratified by baseline. In the stratification, baseline will be divided into quintiles based on the pooled CKD and Healthy subjects in the MITT population. Between group comparison will be carried out at each time point using the CMH test for row mean score difference (RMS) with the modified ridit scores. Analysis will compare the 90 mg group to the 27 mg group at each timepoint overall and for CKD patients and healthy volunteers separately.

Sample SAS code is as follows:

```
PROC FREQ;
  BY visit;
  TABLE base*dose*resp / SCORE=MODRIDIT;
RUN;
```

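### The pooled HV + CKD models compare 9 mg with the higher doses without a population term, and the sample ESTIMATE labelled 90 v 27 mg overall is coded as 9 minus 90 mg

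*SAP*

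**What the plan says.** Under SAP section 3 (and Protocol 9.3), 9 mg is given to healthy volunteers only. The stage 3 and stage 4 CKD cohorts receive 27 and 90 mg.

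SAP 7.6.1 lists three MMRMs for percent change: HV only, CKD only (stages 3 and 4 together), and "A 2-way MMRM pooling stage 3 and stage 4 CKD patients and healthy subjects together". The terms are dose level, visit, "dose-by-visit interaction as factors and baseline response biomarker as covariate". The MODEL statement agrees with the text: the variable `ckd` appears only as a BY variable. Section 7.6.2 reuses the model for absolute change, and the GEE in 7.6.3 has the same terms.

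On output, the SAP says "The difference in LSM between doses and the 95% CI for the difference will also be presented" and "Results will be presented for the pooled population, as well as for the CKD and healthy populations separately". It adds that "LSM for each dose group will be plotted over time for the CKD patients and healthy volunteers pooled population". Section 7.6.3 promises odds ratios between dose levels for the same populations. The sample code requests every pairwise dose difference through `LSMEANS dose / DIFF CL`.

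Dose "is coded as 1 = 9 mg SnPP, 2 = 27 mg SnPP, and 3 = 90 mg SnPP". In the same block stands "ESTIMATE '90 mg v 27 mg overall' dose 1 0 -1". The 168-hour statement below it uses `dose 0 -1 1`.

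**The concern.** In the pooled set, population changes with dose exactly where 9 mg meets the higher doses, and nothing in the model separates the two. If CKD subjects respond differently from healthy volunteers, part of that difference appears as a dose effect in the pooled 27 v 9 and 90 v 9 results and as a step in the pooled dose plots. The SAP presents pooled and HV-only results together and does not say which one answers the optimal-dose objective, so a reader could take the pooled figures as dose-response evidence.

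The coding slip is a separate matter. A row labelled as the one pooled comparison that is balanced by design would hold the confounded comparison, with its sign reversed.

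**Working it through.** **Inputs.** Cohort sizes from SAP section 3; model terms, dose coding and contrasts from SAP 7.6.1 to 7.6.3. No SD, effect size or CKD-HV difference is stated, so those below are assumptions.

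**1. Cohorts.** 3×6 HV + 2×6 CKD 3 + 2×6 CKD 4 = 42, the SAP's own total.

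| Dose | HV | CKD 3 | CKD 4 | CKD share |
|---|---|---|---|---|
| 9 mg | 6 | 0 | 0 | 0/6 |
| 27 mg | 6 | 6 | 6 | 12/18 = 2/3 |
| 90 mg | 6 | 6 | 6 | 12/18 = 2/3 |

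**2. Bias without a population term.** Let δ be the CKD minus HV response at equal baseline. The expected mean at dose d is μ(d) + share(d)×δ. So 27 v 9 and 90 v 9 each carry (2/3 − 0)δ = 0.67δ, and 90 v 27 carries (2/3 − 2/3)δ = 0.

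**3. What baseline absorbs.** Suppose CKD and HV baselines differ by b within-population SDs. The within-dose sum of squares of the CKD indicator is 2×18×(2/3)×(1/3) = 8, and the within-dose df are 42 − 3 = 39. Approximately, bias = (2/3)δ × 39/(39 + 8b²):

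- b = 0: 0.67δ
- b = 1: (2/3)(39/47) = 0.55δ
- b = 2: (2/3)(39/71) = 0.37δ

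**4. Size under assumed shifts.** Simulated single-visit ANCOVA with dose and baseline, no dose effect, two-sided 5% (20,000 replicates at 1 SD, 10,000 otherwise), for 90 v 9; 27 v 9 has the same cell structure:

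| δ (residual SD) | Bias in SD at b = 0, 1, 2 | False-positive rate |
|---|---|---|
| 1 | 0.66, 0.55, 0.36 | 21%, 16%, 10% |
| 0.5 | 0.33, 0.28, 0.19 | 9%, 8%, 6% |
| 0.25 | 0.17, 0.14, 0.10 | 5-6% |

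At δ = 1, the HV-only model or one with a stratum term gives about 5%.

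**5. GEE.** Illustrative responder rates, baseline unrelated to population, no dose effect. HV 10% and CKD 20%: the 27 mg rate is (10+20+20)/3 = 16.7%, so the 27 v 9 odds ratio is 0.200/0.111 = 1.8. HV 20% and CKD 40%: the rate is 33.3%, and 0.50/0.25 = 2.0.

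**6. Correctly coded 90 v 27.** Unbiased if all cohorts fill. If CKD 4 stops after 27 mg, the CKD shares are 6/12 at 90 mg and 12/18 at 27 mg: 1/2 − 2/3 = −1/6 of a common CKD-HV difference. If CKD 3 stops after 27 mg and stage 4 never opens (an assumption; the SAP leaves this to the DSMB), it is 0 − 6/12 = −1/2. With full cohorts and no population term or baseline covariate, the simulated false-positive rate for 90 v 27 is 3.1% at a 1 SD shift and 0.9% at 2 SD. It is conservative because the population difference inflates the residual.

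**7. The contrast.** With levels ordered 9, 27, 90, `1 0 -1` is μ(9) − μ(90). For example means 0, 10, 40 it returns −40, whereas 90 minus 27 is +30. The 168-hour vector takes −1 at 27 mg and +1 at 90 mg on the tenth visit, which is right for three levels. In the CKD run only 27 and 90 mg exist. The first two entries of the two dose vectors are then (1, 0) and (0, −1). Neither sums to zero, so neither is a difference between doses. A rank check confirms that neither is estimable there and that `-1 1` is.

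**The case against.** The strongest reply is that little depends on this.

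- The HV-only model in the same section gives clean 9 mg contrasts, and SAP section 12 repeats all tables by population. This stands and limits the harm, but it does not correct pooled differences, odds ratios and plots that the SAP commits to present.
- There is no formal sample size, no multiplicity scheme and no significance rule, and escalation rests on safety, tolerability and PK. A reader might infer that the pooled 9 mg contrast will drive dose selection; no stated decision rule uses it, so the documents do not support that. The false-positive rates measure distortion, not the risk of a planned decision.
- A reader might also infer from the miscoded line that a correct overall 90 v 27 result would be missing. It would not: "LSMEANS dose / DIFF CL" yields the 27 v 90 difference with its interval. The bad row is a mislabelled copy of the 9 v 90 difference.
- The code is called a sample and could be corrected in programming. True for the contrast; the missing population term is in the SAP text as well.
- The size is assumed. True: if CKD and HV respond alike at equal baseline there is no bias. The simulation is also for a single visit, while `LSMEANS dose` averages over visits. For a shift constant over visits the 2/3 share is the same, but the error rate would depend on within-subject correlation, which is not given.

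**Conclusion.** Both points hold, in a limited form.

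The pooled 27 v 9 and 90 v 9 results in 7.6.1 to 7.6.3 mix dose with population. They carry up to 2/3 of any CKD-HV response difference: at an assumed 1 SD, about 0.36 to 0.67 SD of bias and a 10% to 21% single-visit error rate; at 0.25 SD, close to nominal. This rests on the planned cohort sizes and on a CKD-HV difference that the documents do not give.

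The confounding is partial. It would be too strong to say that 9 mg cannot be compared with the higher doses, because 6 of the 18 subjects at each higher dose are healthy volunteers. The 9 mg LS mean by itself is simply an HV estimate, and pooled 90 v 27, correctly coded, is unbiased if all cohorts fill.

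The ESTIMATE labelled 90 v 27 mg overall is wrong under the SAP's own coding and conflicts with other output from the same code. Both should be fixed before the programs are final.

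**What to change.** 1. State in 7.6.1 to 7.6.3 that comparisons involving 9 mg come from the HV-only model. Limit pooled between-dose LS mean differences, odds ratios and overlaid dose plots to 90 v 27 mg, as 7.6.4 already does for the CMH test.
2. Change the overall ESTIMATE to `dose 0 -1 1` for the pooled and HV runs. Code the CKD run separately with two-level coefficients (`dose -1 1`, and the matching 20 dose-by-visit coefficients at 168 hours).
3. Optionally, add stratum (HV, CKD 3, CKD 4) and stratum-by-visit to the pooled MMRM. This removes between-population variance from 90 v 27 and protects it if a CKD cohort does not fill. It adds 2 + 18 = 20 fixed-effect parameters to the present 31, so name the separate-population models as the fallback if it does not converge.

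**Cost.** SAP wording and programming; no new data. The 9 mg contrasts become less precise: with no population effect the per-visit SE is √(1/6 + 1/6) = 0.577 SD in HV only, against √(1/6 + 1/18) = 0.471 SD in the unadjusted pooled model, a ratio of 1.22. With single-visit ANCOVA df of 14 against 38, the interval is about 30% wider.

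Sparse responder data are not a cost of the change. At assumed rates of 10% or 20%, the chance of 0 of 6 responders at 9 mg at a visit is 0.9⁶ = 53% or 0.8⁶ = 26%, but the same six subjects form the 9 mg group in the pooled GEE now. Where it happens, report responder counts instead of an odds ratio.
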